5.3.2 Exclusion Criteria

Subjects are not eligible for this study if they fulfil one or more of the following exclusion criteria:

- Treatment in the 4 weeks prior to study screening with PZQ, other anti-helminthic, anti-malarial or anti-retroviral compounds or any other medication that might affect the PK of PZQ such as certain antiepileptics (e.g., carbamazepine or phenytoin), glucocorticosteroids (e.g., dexamethasone), chloroquine, rifampicin or cimetidine (see Section 6.5.2 and Biltricide® SPC)For children being breast fed, treatment of the mothers/wet nurses with PZQ in the 3 days prior to administration of IMP
- Previous history of adverse reactions associated with PZQ treatment
- History of acute or severe chronic disease, including hepato-splenic schistosomiasis
- Marked increases of the liver transaminases (alanine aminotransferase and/or aspartate aminotransferase) above 3x ULN
- Fever defined as temperature above 38.0°C
- Debilitating illnesses such as tuberculosis, malnutrition, etc. as well as a medical history of seizures
- Mixed S. haematobium and S. mansoni infections
- Findings in the clinical examination of schistosome-infected children participating in the study as performed by the study clinician on the treatment day, that in the opinion of the

Investigator constitutes a risk or a contraindication for the participation of the subject in the study or that could interfere with the study objectives, conduct or evaluation

• Unlikelihood to comply with the protocol requirements, instructions and trial-related restrictions, e.g., uncooperative attitude, inability to return for follow-up visits, and improbability of completing the trial

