8.5.4 Analysis of Safety and Other Endpoints

Values for all safety variables will be listed by subject and time point. Where appropriate, safety variables will be summarized using descriptive statistics.

Adverse events (AEs) will be coded by the Medical Dictionary for Regulatory Activities (MedDRA) preferred terms, and all summary tables for AEs will be organized by these categories. Frequency counts and percentages will be presented for subjects with at least 1 treatment emergent AE within each system organ class and preferred term, separated by treatment group. Treatment-emergent AEs will also be summarized by relationship to treatment and by severity within each treatment group.

By-patient listings of clinical laboratory data and vital signs will include indications of value that are outside the reference ranges, and values that are clinically significant. Tables describing out-of-reference range shifts will be provided for clinical laboratory test results and vital signs as appropriate and by treatment arm.

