## 17.3 Clinical Laboratory Evaluation

Laboratory values (including corresponding normal ranges) will be used for summary statistics and shift tables.

Quantitative data will be examined for trends using descriptive statistics (mean, SD, median, Q1, Q3, minimum, and maximum) of actual values and changes from baseline to each visit over time. The changes computed will be the differences from baseline (Day 1 samples) to end-of-trial (Day 14 / early withdrawal). Qualitative data based on reference ranges will be described according to the categories (i.e. Low, Normal, High). Only the 'high' and 'low' categories will be flagged. The number of subjects with clinical laboratory values below, within, or above normal ranges at baseline compared to endpoint will be tabulated for each test by treatment. Shift tables of baseline versus endpoint (as well as the worst value at any post-baseline visit) will be presented. In case of missing data LOCF will be applied.

Laboratory values that are outside the normal range will also be flagged in the data listings, along with corresponding normal ranges. Any out-of-range values that are identified by the investigator as being clinically significant will be shown in a data listing.

Baseline (Day 1) is the last measurement prior to the first dose of any trial treatment.

Subjects without post baseline laboratory samples will be excluded from analyses with respect to change from baseline summaries.

Data will also be presented for absolute and change from baseline results using boxplots, by time point/visit.

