#### MSC1028703A and MSC2499550A

#### MS200661-0005

Parameter	Age	Low	Normal	High
Heart rate	3-<12-months	<100	100-180	>180
[beats/min]	12-24-months	<90	90-160	>160
	2 - <6 years	<80	80 - 140	>140
Oral Temperature [°C]	3-month - <6 years	<35.5	35.5 - 37.5	>37.5

Quantitative data will be examined for trends using descriptive statistics (mean, SD, median, Q1, Q3, minimum, and maximum) of actual values and changes from baseline to each visit over time. Baseline will be defined as the Day 1 pre-dose vital signs measurement.

Subjects data will be listed by cohort, subject and time point. An additional subject data listing will present all changes from baseline reported. Data will also be presented for absolute and change from baseline results using boxplots, by time point/visit.

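### The AST/ALT shift tables have a single class above normal, so no planned table counts, by cohort, the children who newly exceed the trial's own 3x ULN limit

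*SAP*

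**What the plan says.** SAP 17.3 (Clinical Laboratory Evaluation) sets the classes: "Qualitative data based on reference ranges will be described according to the categories (i.e. Low, Normal, High". It then plans a count of children on these classes: "clinical laboratory values below, within, or above normal ranges at baseline compared to endpoint will be tabulated for each test by treatment". It adds: "Shift tables of baseline versus endpoint (as well as the worst value at any post-baseline visit) will be presented". The reference value is defined as follows: "Baseline (Day 1) is the last measurement prior to the first dose of any trial treatment". Section 17.3 defines no class in multiples of ULN and no grade above High.

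Protocol 5.3.2 lists as an exclusion: "Marked increases of the liver transaminases (alanine aminotransferase and/or aspartate aminotransferase) above 3x ULN". AST and ALT are both in the biochemistry panel (Protocol, Annexe IV). Protocol 8.5.4 plans the same kind of output as the SAP: "Tables describing out-of-reference range shifts will be provided for clinical laboratory test results and vital signs".

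SAP 17.3 also plans:
- mean, SD, median, quartiles, minimum and maximum of values and of changes from baseline;
- boxplots;
- listings that flag out-of-range values and show the normal range;
- a listing of out-of-range values that the investigator judges clinically significant.

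**The concern.** The boundary of the highest reporting class (1x ULN) lies well below the level that the protocol itself treats as a marked transaminase increase (3x ULN). Two losses follow in the shift tables. Children who enter in the gap between the two limits have no higher class to move to. Among children who enter normal, a trivial rise and a large one look alike.

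The primary objective of Part 1 is to find a dose with a clinically meaningful cure rate and an acceptable safety profile. Under Protocol 8.6 the SMC uses the Part 1 safety and efficacy data to recommend the dose for infants in Part 2. The protocol also gives the liver specific attention: transaminases are an entry criterion, and a liver-related adverse event triggers an extra Day 8 blood sample (Protocol 6.5.5 and 7.1.4). Two dose cohorts could have identical AST/ALT shift tables although one had only rises just over the normal limit and the other had rises past 3x ULN.

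**Working it through.** **1. No plan figure to reproduce.** The plan attaches no sample size, power or error rate to these tables. The check compares cut-points, followed by a rough size under stated assumptions.

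**2. Inputs.**
- High: above the normal range, i.e. more than 1x ULN (SAP 17.3).
- Excluded at entry: more than 3x ULN (Protocol 5.3.2).
- Eligible and already High at baseline: more than 1x and up to 3x ULN.
- Cohort size: 60 per Part 1 arm (SAP 6.1).

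**3. Pre-dose and post-dose pairs**, in multiples of ULN. All are eligible at entry.

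| Baseline to post-dose | Planned classes | With an added class above 3x ULN |
|---|---|---|
| 0.8 to 1.1 | Normal to High | Normal to 1-3x |
| 0.8 to 10 | Normal to High | Normal to above 3x |
| 1.5 to 1.6 | High to High | 1-3x to 1-3x |
| 1.5 to 10 | High to High | 1-3x to above 3x |
| 2.9 to 3.1 | High to High | 1-3x to above 3x |
| 3.0 to 30 | High to High | 1-3x to above 3x |

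The planned classes put the first two pairs in one cell and the last four in another. One extra cut at 3x ULN separates the pairs that end above 3x from those that do not. This step needs no assumed data.

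**4. How many children could start High.** The documents give no baseline AST/ALT values, so this step is an assumption. Take ALT/ULN as log-normal with median m and log-SD s:

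P(1 < ALT/ULN ≤ 3) = Φ(ln(3/m)/s) − Φ(ln(1/m)/s)

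- m = 0.5, s = 0.4: Φ(4.479) − Φ(1.733) = 1.0000 − 0.9584 = 4.2%; × 60 = 2.5 children.
- m = 0.6, s = 0.5: Φ(3.219) − Φ(1.022) = 0.9994 − 0.8465 = 15.3% (rounded after subtraction); × 60 = 9.2.
- m = 0.8, s = 0.4: Φ(3.304) − Φ(0.558) = 0.9995 − 0.7115 = 28.8%; × 60 = 17.3.
- m = 0.8, s = 0.5: Φ(2.644) − Φ(0.446) = 0.9959 − 0.6723 = 32.4%; × 60 = 19.4.

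Over m = 0.5 to 0.8 and s = 0.4 to 0.5 the share runs from 4% to 32%, about 2 to 19 of 60.

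**5. Without a distribution.** If a share p of children starts between 1x and 3x ULN, the chance of at least one in a cohort of 60 is 1 − (1 − p)^60. For p = 2% this is 1 − 0.98^60 = 0.70; for p = 5% it is 1 − 0.95^60 = 0.95. Even a small share makes it likely that a cohort contains such a child.

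Steps 4 and 5 count children who start High. They do not say how many of them then rise past 3x ULN, and nothing in the documents allows that to be estimated.

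**The case against.** The strongest reply is that the signal is not lost. A rise from 2x to 10x ULN would appear in its cohort's maximum value and maximum change, in the boxplots, and as a flagged entry in the listing. Protocol 7.4.1.1 also gives increased ALT as an example of a condition to be reported as an adverse event when the abnormality is symptomatic, leads to discontinuation or is considered medically important. SAP 17.1.1 tabulates treatment-emergent events by cohort. This stands: the plan would not hide an individual large rise. It does not supply the count. A maximum shows one child per cohort, a listing is not a summary, and the adverse-event route depends on the investigator's judgement in an open-label trial.

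A second reply is that SMC outputs are set in the SMC charter, which is not among these documents. It may ask for counts above a multiple of ULN. That also stands, so the point concerns the tables planned in the SAP and not what the SMC will see.

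Readers might infer more than the documents support:
- **That any marked rise is missing from the shift tables.** This is so only for children already High at baseline. A child normal at baseline still shows Normal to High, without the size of the rise.
- **That the plan is inconsistent.** Reference-range shifts are what Protocol 8.5.4 promises, and a normal limit and an exclusion limit serve different purposes.
- **That temperature has the same fault**, because SAP 17.4 starts High above 37.5 °C while the protocol has "Fever defined as temperature above 38.0°C". SAP 17.4 names no vital-sign shift table, and Protocol 8.5.4 plans one only as appropriate. The SAP row is for oral temperature, whereas the protocol states no route.
- **That the NCI-CTCAE entry in the SAP's abbreviation list commits the sponsor to toxicity grading.** An unused abbreviation does not, and Protocol 7.4.1.1 sets a different scale for adverse-event severity.

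**Conclusion.** The point holds as a limited gap in reporting for AST and ALT. It follows directly from the two cut-points. Children who enter at more than 1x and up to 3x ULN cannot register a further rise in the planned shift tables. Rises of very different size from a normal baseline share one cell. No planned table gives the number of children per cohort newly above 3x ULN.

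The size is uncertain. Under the assumed log-normal values, 4% to 32% of children (about 2 to 19 of 60) would start High; the true share cannot be read from the documents. This bounds how many children the High-to-High problem could touch. It is not an estimate of missed liver signals. The gap does not invalidate the safety analysis. Closing it is a cheap improvement that would make the safety comparison between doses more informative.

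**What to change.** In SAP 17.3 keep the Low/Normal/High tables and add, for each cohort:
- a shift table for AST and one for ALT (one table shell) with classes ≤1, >1 to 3 and >3x ULN, from baseline to the worst post-dose value;
- the number and percentage of children with a new value above 3x ULN.

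State that the worst post-dose value comes from Day 2, or from Day 8 where a sample was taken. The protocol's Appendix II schedules routine post-dose safety laboratory tests on Day 2 and adds Day 8 only when adverse-event follow-up requires it. For most children the worst value will therefore be the Day 2 value, so a separate Day 2 table is not needed.

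The 3x ULN cut is the trial's own limit, used here only as a reporting class; no eligibility or clinical rule changes. The values and normal ranges are already collected. The cost is a few lines of SAP text and one extra table.

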## 17.4 Vital Signs

Vital signs including blood pressure (BP), pulse rate (PR) and body temperature will be assessed according to the trial schedule. Vital signs will be considered abnormal as follows:

Parameter	Age	Low	Normal	High
Systolic blood pressure	3 - <12-months	<72	72 - 104	>104
[mmHg]	12-24-months	<86	86 - 106	>106
	2 - <6 years	<89	89 - 115	>115
Diastolic blood pressure	3- <12-month	<37	37 - 56	>56
[mmHg]	12-24-months	<42	42 - 63	>63
	2 - <6 years	<46	46- 76	>76

#### MSC1028703A and MSC2499550A

#### MS200661-0005

Parameter	Age	Low	Normal	High
Heart rate	3-<12-months	<100	100-180	>180
[beats/min]	12-24-months	<90	90-160	>160
	2 - <6 years	<80	80 - 140	>140
Oral Temperature [°C]	3-month - <6 years	<35.5	35.5 - 37.5	>37.5

Quantitative data will be examined for trends using descriptive statistics (mean, SD, median, Q1, Q3, minimum, and maximum) of actual values and changes from baseline to each visit over time. Baseline will be defined as the Day 1 pre-dose vital signs measurement.

Subjects data will be listed by cohort, subject and time point. An additional subject data listing will present all changes from baseline reported. Data will also be presented for absolute and change from baseline results using boxplots, by time point/visit.

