3.4 Clinical evidence to date

3.4.1 Clinical data in adults

Over 40 years of treatment with PZQ racemate tablets showed a good safety and tolerability profile in previous trials, in the recent meta-analysis in children and adults conducted by the WHO [11] and according to the current Periodic Safety Update Reports (PSURs). The recent phase I studies (EMR200661-001 and EMR200585-001) confirmed the good safety profile for rac-PZQ ODTs and L-PZQ ODTs in adults.

The most common and known side effects of PZQ treatment are associated with gastrointestinal effects: diarrhea, nausea, vomiting and abdominal pain. Although also transient neurological effects have been recorded (headache and dizziness), dizziness was not observed after L-PZQ ODTs administration in the phase I study. Regarding the general disorders the following adverse events have been reported: weakness, fatigue and increased body temperature. All these symptoms are usually transient, and spontaneously resolve. Adverse reactions, including hypersensitivity reactions, may partly represent endogenous reactions to the killing off of the parasites by PZQ, and were not observed in the phase I study with L-PZQ or rac-PZQ ODTs in healthy volunteers.

For patients suffering schistosomiasis, this underlying parasitosis could also mask the adverse events of PZQ treatment, e.g., Katayama syndrome, which is an early clinical manifestation of

schistosomiasis occurring several weeks post-infection with *Schistosoma spp* (trematode) worms. The disease onset appears to be related to migrating schistosomula and egg deposition with individuals typically presenting with nocturnal fever, cough, myalgia, headache, and abdominal tenderness [10].

It is frequently not clear whether the complaints reported by patients or adverse effects determined by the doctor have been caused directly by PZQ (I, direct relationship), whether these are to be regarded as an endogenous reaction to the killing off of the parasites by PZQ (II, indirect relationship) or else represent signs and symptoms of the parasitic infection (III, no relationship). It is often difficult to reliably differentiate between possibilities I, II and III (Master SPC for PZQ, dated 22 Feb 2013).

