Abnormal laboratory findings and other abnormal investigational findings (e.g., on an ECG trace) should not be reported as AEs unless they are associated with clinical signs and symptoms, lead to treatment discontinuation or are considered otherwise medically important by the Investigator. If a laboratory abnormality fulfils these criteria, the identified medical condition (e.g., anaemia, increased ALT) must be reported as the AE rather than the abnormal value itself.

Serious Adverse Events

An SAE is any untoward medical occurrence that at any dose:

Results in death

Is life-threatening. (Note: The term "life-threatening" refers to an event in which the subject is at risk of death at the time of the event, not an event that hypothetically might have caused death if it was more severe.)

Requires inpatient hospitalization or prolongs an existing hospitalization

Results in persistent or significant disability or incapacity

Is a congenital anomaly or birth defect

Is otherwise considered to be medically important

Note: Important medical events that may not result in death, be life-threatening, or require hospitalization may be considered as SAEs when, based upon appropriate medical judgment, they may jeopardize the subject or may require medical or surgical intervention to prevent one of the outcomes listed above. Examples of such events include allergic bronchospasm requiring intensive treatment in an emergency room or at home, blood dyscrasias or convulsions that do not result in inpatient hospitalization, or the development of drug dependency or drug abuse.

For the purposes of reporting, any suspected transmission of an infectious agent via an IMP is also considered an SAE, as described in Section 7.4.1.4.

Events that Do Not Meet the Definition of an SAE

Elective hospitalizations to administer, or to simplify trial treatment or trial procedures (e.g., an overnight stay to facilitate chemotherapy and related hydration therapy application) are not considered SAEs. However, all events leading to unplanned hospitalizations or unplanned prolongation of an elective hospitalization (e.g., undesirable effects of any administered treatment) must be documented and reported as SAEs.

Events Not to Be Considered as AEs/SAEs

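### SAP 17.4 sets Low, Normal and High limits for vital signs but uses them in no table or flag, although protocol 8.5.4 says vital-sign shift tables by arm will be provided.

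*SAP*

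**What the plan says.** Protocol 8.5.4 makes two commitments on vital signs. The first concerns tables: "Tables describing out-of-reference range shifts will be provided for clinical laboratory test results and vital signs as appropriate and by treatment arm". The second concerns listings: "By-patient listings of clinical laboratory data and vital signs will include indications of value that are outside the reference ranges". Changes in vital signs, with temperature, blood pressure and pulse rate named, are a listed safety endpoint (protocol 8.3.3; SAP 17).

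SAP 17.4 opens with "Vital signs will be considered abnormal as follows" and gives Low, Normal and High limits: by age band for blood pressure and heart rate, and as one row for oral temperature (High is above 37.5 °C). The planned output then follows. For tabulated output: "Quantitative data will be examined for trends using descriptive statistics (mean, SD, median, Q1, Q3, minimum, and maximum) of actual values and changes from baseline". For listings: "Subjects data will be listed by cohort, subject and time point", plus a listing of changes. For graphs: "Data will also be presented for absolute and change from baseline results using boxplots, by time point/visit". The limits are not mentioned again.

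SAP 17.3, for laboratory tests, begins with the same continuous summaries. It goes on to counts below, within and above range by treatment, shift tables that include the worst post-baseline value, and flagged listings. SAP 9 states that the protocol's statistical methods were adopted.

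**The concern.** The SAP defines what counts as abnormal and then specifies a method that never counts it. Sections 17.3 and 17.4 start alike and only the laboratory section goes on to categories, so this reads as an omission rather than a decision.

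At stake is the rate, per arm, at which children move out of range on a named safety endpoint in a dose-finding study. The protocol lists "weakness, fatigue and increased body temperature" among the events reported after praziquantel, so temperature is not an idle variable here. If a few children in one arm have an excursion and the rest do not, mean and median changes barely register it.

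**Working it through.** No figure in the documents is in dispute. The check is a comparison of sections, followed by an illustration of scale.

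**1. Sections side by side**

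| Output | Protocol 8.5.4 | SAP 17.3 (laboratory) | SAP 17.4 (vital signs) |
|---|---|---|---|
| Continuous summaries | Where appropriate | Yes | Yes |
| Counts Low/Normal/High | Not specified | Yes, by treatment | None |
| Out-of-range shift tables | Both data types, by arm, where appropriate | Yes, including worst value | None |
| Out-of-range flags in listings | Both data types | Yes | None stated |

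**2. Whether another section supplies the count**

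- SAP 11 has a general rule that qualitative variables get frequencies and percentages. Section 17.4 never makes the Low/Normal/High category an analysis variable, and the rule would not produce a shift table.
- Treatment-emergent adverse events are tabulated by cohort (SAP 17.1.1). However, protocol 7.4.1.1 says abnormal investigational findings "should not be reported as AEs unless they are associated with clinical signs and symptoms", lead to discontinuation, or are judged otherwise medically important. The study is open label (protocol 6.10), so that judgement can be made with the arm known. A count against fixed limits does not depend on it.

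**3. Scale (assumed, not from the documents)**

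Input from the documents: n = 60 per Part 1 arm (SAP 6.1). Assumed: x = 3, 6 or 9 children rise by d = 1.0, 1.5 or 2.0 °C; every one of them goes from Normal to above 37.5 °C; all other children are unchanged.

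Mean change = x × d / 60. For x = 6 and d = 1.5, this is 9 / 60 = 0.15 °C.

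Exact (Clopper-Pearson) 95% limits for x/60: the lower limit is the 2.5% point of Beta(x, 61 − x), and the upper is the 97.5% point of Beta(x + 1, 60 − x).

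| x | Mean change at d = 1.0 / 1.5 / 2.0 °C | Count, exact 95% CI |
|---|---|---|
| 3 | 0.05 / 0.075 / 0.10 | 5.0% (1.0% to 13.9%) |
| 6 | 0.10 / 0.15 / 0.20 | 10.0% (3.8% to 20.5%) |
| 9 | 0.15 / 0.225 / 0.30 | 15.0% (7.1% to 26.6%) |

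Three things follow.

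- The same mean change of 0.15 °C arises from 6 children at 1.5 °C and from 9 children at 1.0 °C, so the mean does not identify the rate.
- At most 15% of the arm has changed, which is under a quarter, so the median and upper quartile of change both stay at zero.
- The maximum change equals d whether 3 or 9 children are affected.

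**4. Why a shift table and not only a count**

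Protocol 5.3.2 excludes children above 38.0 °C, while SAP 17.4 calls anything above 37.5 °C High. A child between those values can be dosed already High. Only a baseline-to-post-dose table separates new excursions from existing ones.

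**5. Whether the limits classify every child**

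All SAP 17.4 limits stop below 6 years. Part 1 enrols children aged 2 to 6 years (protocol 5.3.1), and the SAP 10.2.1 subgroup includes age 6. A child who has turned 6 has no stated limit.

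**The case against.** The strongest reply is that little is lost. The protocol commitment is qualified by appropriateness. SAP 9 adopts the protocol's methods, so the tables have not been withdrawn. Protocol 7.4.1.2 records any unfavourable change in a child's condition as an adverse event, and fever may itself be a clinical sign. All the data are collected and listed.

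Part of this stands. The protocol does not mandate a particular layout, and symptomatic fever would normally reach the adverse-event tables. But the SAP gives no reason why shift tables would be inappropriate for vital signs, prints limits that feed nothing, and leaves excursions without symptoms to individual judgement.

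A reader might infer more than the documents support:

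- **That excursions would be visible only in listings or as boxplot outliers.** Minimum, maximum and quartiles are tabulated, so extremes do reach a summary table. The count does not.
- **That the Safety Monitoring Committee would lack rates by dose.** Its outputs are specified in its charter, which is not among the documents.
- **That the means mix age bands.** Analyses are by treatment group. C1 to C7 enrol ages 2 to 6 years, C8 13 to 24 months and C9 3 to 12 months, so each sits almost wholly in one band; only a 12-month-old in C9 crosses a stated boundary. Temperature has a single limit.
- **That High means fever.** The SAP's 37.5 °C is not the protocol's exclusion threshold of 38.0 °C.
- **That the 6/60 example is a forecast.** A 1.5 °C rise from 35.9 to 37.4 °C stays Normal; the example holds only if all six children cross the limit.

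**Conclusion.** The point holds as a mismatch between protocol and SAP that has a consequence for the results. Protocol 8.5.4 says vital-sign shift tables and flagged listings will be provided; SAP 17.4 plans neither and declares no departure. As written, the analysis can show that an extreme value exists, but not how many children in each arm moved out of range, and adverse-event tables cover that only in part.

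Its practical size cannot be taken from the documents. Under the stated assumptions, 5% to 15% of an arm of 60 could cross a limit while the mean moves only 0.05 to 0.30 °C. The efficacy analysis is unaffected and no data are lost, so this is a correction to the planned tables and not a design fault.

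**What to change.** In SAP 17.4, for temperature, blood pressure and pulse, add by cohort:

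- the number and percentage of children Low, Normal and High at each scheduled time;
- a baseline-to-post-dose shift table at 8 hours, at Day 2 where measured (Appendix II schedules it for C8 and C9 only), and at Day 14-21;
- out-of-range flags in the listings, as protocol 8.5.4 says.

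The exact layout is a proposal modelled on SAP 17.3; the protocol does not dictate it. With only two scheduled post-dose readings in C1 to C7, tables by time point suffice and a separate worst-value table would add little.

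Alternatively, state in SAP 9 that the vital-sign shift tables and flags are dropped, and why.

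Before tabulating, reconcile the limits, which stop below 6 years, with the enrolled range of 2 to 6 years, so that every child can be classified. Label the High temperature category by its SAP limit and not as fever.

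The cost is a few extra tables from data already collected, plus settling the limits for 6-year-olds.
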